3.2.3 Exclusion criteria

Exclusion criteria are:

- any orthopaedic surgery or other surgical interventions that might influence mobility in the past six months;
- Botulinum Toxin A injections in the past three months;
- intrathecal Baclofen (ICB) therapy in the last six months or selective dorsal rhizotomy (SDR) in the past year;
- impairments that could contra indicate fitness testing;
- plantarflexion contractures;
- a knee flexion contracture > 10°;
- hip endorotation ≤20° in midstance;
- other medical conditions influencing mobility;
- severe behavioural problems.

3.2.4 Sample size calculation

Sample size is based on power analyses on the expected changes in the primary outcome 'walking efficiency'.

Walking efficiency, assessed with a portable gas-analysis system, will be defined as the EC of walking $(J^{-1} \cdot kg^{-1} \cdot m^1)$. Based on previous research, EC of walking in children with CP is

shown to be 30-50% higher, compared to healthy children (10-12). CP children with GMFCS levels I and II show a mean net EC of walking of 5.02 (±1.70) J⁻¹·kg⁻¹·m¹ (29). Based on previous research on the effectiveness of AFOs of children with CP (28;29), a reduction of 25% from this value (\approx 1.26 J⁻¹·kg⁻¹·m¹) is chosen as a clinical significant change. Based on these values, a standardized difference for within-subject studies can be calculated using the following formula: N = 2SD² (Z α + Z β)²/ Δ^2 (59). Assuming a power of 80% and a significance level of 0.05, a sample size of 29 patients is needed to detect a difference of 25% in net EC of walking. A sample size of 32 is chosen to allow for dropout and for a sufficient sample for regression analysis.

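### The sample size in Protocol 3.2.4 is labelled within-subject but uses a between-child SD, so 29 children and 80% power do not describe this single-group pre-post design; the error is conservative for the 25% target

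*Protocol*

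**What the plan says.** Section 3.2.4 bases the sample size on walking efficiency, measured as net energy cost of walking. It takes a mean of 5.02 and an SD of 1.70 from earlier work in children at GMFCS levels I and II. It chooses "a reduction of 25% from this value", about 1.26, as the clinically significant change.

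It then states that "a standardized difference for within-subject studies can be calculated using the following formula" and gives N = 2SD²(Zα+Zβ)²/Δ². With 80% power and a significance level of 0.05 it concludes that "a sample size of 29 patients is needed to detect a difference of 25% in net EC of walking". Enrolment is set at 32 to cover dropout and to leave enough children for regression.

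Section 3.1 describes a pre-post experimental study, without a parallel control group. Section 3.6.2 compares the three stiffness configurations by repeated measures ANOVA. Section 3.6.3 compares baseline with the later visits by a linear mixed model for repeated measures. No within-child correlation and no SD of the change is given.

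**The concern.** The label and the input do not fit together. When each child is its own control, the variance that matters is that of the child's change. For equal SDs at the two visits this is 2SD²(1−ρ), where SD is the between-child SD and ρ the correlation between the two measurements. The printed formula has 2SD² without the factor (1−ρ). With a between-child SD that is the two-independent-groups formula, and its result is a number per group.

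The same expression can be valid for paired data if SD is the within-child SD. As section 3.2.4 describes it, 1.70 is not that: it is the spread around the mean of a group of children.

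This paragraph is the protocol's only justification of its sample size. As written, it tells the reader that 29 children are required and that power is 80%. Neither follows for this design, and the difference the study could detect is not stated.

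**Working it through.** **Inputs from section 3.2.4.** Mean 5.02; SD 1.70; Δ = 0.25 × 5.02 = 1.255, stated as about 1.26; power 80%; significance level 0.05, sidedness not stated. **Assumed:** ρ from 0 to 0.8, and the same SD at both visits.

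**1. Reproduce the 29.** With Zα = 1.96 (two-sided) and Zβ = 0.8416:

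2 × 1.70² × (1.96 + 0.8416)² / 1.26² = 28.6, rounded up to 29.

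Δ = 1.255 gives 28.8, again 29. A one-sided test gives 22.5, so 23, which does not match. The multiplication is right, and the test is evidently two-sided. The 29 is the size of each of two independent groups.

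**2. Paired form.** SDdiff = 1.70 × √(2(1−ρ)) and N = SDdiff²(Zα+Zβ)²/Δ². At ρ = 0, SDdiff² = 2SD² and the two formulas coincide. At ρ = 0.5, SDdiff = 1.70 and N = 28.6 × 0.5 = 14.3, so 15. The paired t-test figures below use the noncentral t distribution with Δ = 1.26 and two-sided 0.05.

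| ρ (assumed) | SDdiff | N, normal approx. | N, paired t | Power at n = 29 |
|---|---|---|---|---|
| 0 | 2.40 | 29 | 31 | 78% |
| 0.25 | 2.08 | 22 | 24 | 88% |
| 0.5 | 1.70 | 15 | 17 | 97% |
| 0.7 | 1.32 | 9 | 11 | 99.9% |
| 0.8 | 1.08 | 6 | 8 | >99.9% |

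With 29 children the paired t-test reaches 80% power for 25% once ρ exceeds about 0.06.

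**3. Difference detectable with 80% power, as a percentage of 5.02.**

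| ρ (assumed) | n = 29 | n = 32 |
|---|---|---|
| 0 | about 26% | about 24% |
| 0.5 | about 18% | about 17% |
| 0.7 | about 14% | about 13% |
| 0.8 | about 12% | about 11% |

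**4. Size of the target against the protocol's own comparison.** Section 3.2.4 says that energy cost in CP is "shown to be 30-50% higher, compared to healthy children". If that excess applies to the net value of 5.02, the healthy value is 5.02/1.5 = 3.35 to 5.02/1.3 = 3.86. A fall of 1.26 leads to 5.02 − 1.26 = 3.76, which lies inside that range. The protocol does not say whether the excess is in net or gross energy cost, so this step is conditional.

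**The case against.** The strongest reply is that nothing is lost. The calculation multiplies out correctly, and ρ = 0 is close to the worst case for a child measured twice. A protocol that has no reliable ρ may reasonably use a conservative bound. Enrolment of 32 also rests on dropout and regression. All of this stands, and it limits the point to a mismatch between formula, SD and design. It does not rescue the text: the 29 is presented as a within-subject requirement, not as a bound, and the assumption behind it is not stated.

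Four stronger readings are tempting, and the document does not support them.

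- *The trial is underpowered.* For 25% it is not, at any clearly positive ρ.
- *Because the calculation is conservative, gains of 10–15% are within reach.* With all 32 children and ρ = 0.5, power is 68% for 15% and 37% for 10%. At ρ = 0.8 it is 97% and 73%. The answer depends on a ρ that the protocol does not give, and section 3.5.3 says withdrawn children are not replaced.
- *The trial can only see a 25% effect.* The difference used for power is not the significance threshold. Even at ρ = 0 with 29 children, an observed mean fall of about 18% would reach p < 0.05 (2.05 × 2.40/√29 = 0.91; 0.91/5.02 = 18%).
- *The target is near-normalisation and therefore unrealistic.* Besides the net-or-gross question, the 5.02 comes from GMFCS I–II, while section 3.2.2 admits I–III and only flexed-knee gait, which the introduction describes as often very costly in energy. The 25% is attributed to earlier AFO studies that cannot be examined here.

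**Conclusion.** The point holds in a limited form. Section 3.2.4 uses a between-child SD in a formula called within-subject, and the stated 29 patients and 80% power are not properties of the single-group pre-post design. Over assumed ρ from 0 to 0.7 the paired t-test needs 31 down to 11 children, and 29 children give 78% to 99.9% power.

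The slight shortfall at ρ = 0 comes from using the normal approximation instead of the t distribution. Beyond ρ of about 0.06 the error works in the trial's favour for the 25% target.

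These figures assume equal SDs at the two visits, a two-sided test and a simple baseline-to-follow-up comparison. The paragraph should be corrected because its statement is wrong as written, but neither enrolment nor the conduct of the trial depends on the correction.

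**What to change.** Rewrite the calculation in section 3.2.4:

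- Use N = SDdiff²(Zα+Zβ)²/Δ², with SDdiff = SD × √(2(1−ρ)), and state that the test is two-sided.
- State the assumed SD of the pre-post change and its source, or show a range of ρ. Data from children measured before and after AFO treatment are preferable. Test-retest reproducibility alone (references 11 and 12 appear to be of this kind) would tend to overstate ρ. The energy cost test at casting and the long-term visit lie about 28 to 48 weeks apart (4 weeks to delivery, three periods of 4–8 weeks, then 12–20 weeks), and response to the orthosis differs between children.
- Keep 32 children. In place of the statement that 29 are needed, give the power for 25% and the difference detectable with 80% power at n = 29 and n = 32, as tabulated above.
- If the 25% is compared with healthy children, say whether the 30–50% excess refers to net energy cost.

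The cost is one paragraph. Enrolment, visits and analyses do not change.

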3.3 Investigational product/treatment

For children with CP, current AFO prescription is primarily based on the patient's gait deviations. AFO prescription for patients walking with excessive knee flexion is diverse, but anterior leaf spring (ALS) orthoses are commonly prescribed (23). This AFO type is also known as the Floor Reaction Orthosis (FRO), and is usually composed out of a stiff material, such as carbon fibre. Since this study will only enrol patients who walk with a flexed knee gait pattern, most baseline AFOs (control condition) will be FROs with a rigid footplate that are made out of carbon.

Follow-up AFOs will be manufactured following the Mälmo-technique (Otto Bock HealthCare GmbH, Duderstadt, Germany). Within this method, orthoses are composed out of pre-preg materials (e.g. impregnated carbon fibres). By applying these materials, orthoses are much stronger and have more favourable mechanical properties, compared to conventional orthoses that are made of carbon (or poly-propylene) (63). For fair evaluation of AFO efficacy, the global design of the AFOs will be similar for all subjects. Hence, follow-up AFOs (case condition) will be FROs with a rigid footplate made out of carbon composite.

Neuro Swing[®] configurations

Follow-up AFOs will be fabricated with an integrated 'Neuro Swing[®] system' ankle joint (CE-certified product), which has recently been developed by Fior & Gentz (Lüneberg, Germany). Due to the system's adjustable spring force (stiffness), alignment and range of motion (ROM) of the ankle joint, AFO properties can be varied within the same orthosis. The benefit of using this system is that it prevents multiple AFO manufactures within subjects. Since this study primarily investigates the effects of varying stiffness, the Neuro Swing[®] system will be configured into three different levels of stiffness (rigid, stiff, and flexible), whereas other mechanical properties will be kept equal for each configuration.

The Neuro Swing[®] ankle joint comes with five spring packages with different forces. The ankle joint can be adjusted with different springs (stiffness) towards plantar and dorsal flexion. In this study, the anterior spring (dorsal flexion) will be varied, while the posterior spring (plantar flexion) will be the same for each configuration. This posterior spring will be a spring with low forces.

The rigid configuration of the Neuro Swing[®] system will not allow any dorsal or plantar flexion during walking, while the stiff and flexible configuration of the Neuro Swing[®] system will. For stiff configuration, the ankle joint system will be equipped with the spring that best approaches the stiffness of the subject's baseline AFO. For the flexible configuration, the system will be equipped with a spring that is less stiff (if the spring of the stiff configuration is the "fifth" (strongest), the flexible AFO will be configured with the "fourth" spring of the Neuro Swing[®] package).

Tuning

To further ensure fair comparison of AFO efficacy of different configurations, tuning of AFO-footwear combination (AFO-FC) should be done adequately and similarly for each AFO configuration. Tuning involves modification of the alignment of the AFO-FC in order to optimize gait kinetics and kinematics (64). The position of lower limb segments is described relative to the force of gravity, which acts vertically. The angle of the segment relative to the vertical, referred to as shank to vertical angle (SVA), can be expressed in degrees of incline or recline from the vertical (65). Most efficient gait is assumed to be achieved with a optimal SVA in midstance, which should be 10-12° inclined. Owen (65) recently introduced a clinical algorithm for the design and tuning of AFO-FCs, aiming to achieve the most optimal SVA. By using this algorithm for each AFO prescription, it is assumed that tuning of each AFO-FC will be adequate and for each AFO configuration.

3.4 Study parameters/endpoints

This study will evaluate the efficacy of AFOs in CP, using outcome measures at the ICF components of 'body functions and structures' and 'activities and participation' (45). All measurements are summarized in table 2 and further explained below.

| | | Baseline | | | Follow-up | | |
|-----------------|------------------|-------------------------------|-------------------|------------|-----------------------|-------------------|--------------------|
| | | Bare foot, shoes & old AFO-FC | | New AFO-FC | | | |
| | | T0 _{cast} | T0 _{fit} | | T0 _{deliver} | T1 _k * | T2 _{kopt} |
| | Time interval** | | -2 | +2 | +4-8 | +12- | |
| Primary study p | | | | | | | |
| Activities and | SAM*** | | | | Х | Х | х |
| participation | ECWT | Х | | | | Х | х |
| Secondary stud | ly parameters | | | | | | |
| Body functions | 3D-gait analysis | | | | х | Х | х |
| and structures | Physical fitness | | v | | | | |
| | test | | Х | | | | |
| Activities and | CAPE*** | | | | х | | х |
| participation | CAFE | | | | X | | ~ |
| Other study par | ameters | | | | | | |
| Environmental | Intake | x | | | | | |
| and personal | questionnaire | ^ | | | | | |
| factors | BSS | Х | | | | | |
| | Physical | V | | | | | |
| | examination | Х | | | | | |
| | FAQ | Х | | | | Х | х |
| | FMS | Х | | | | х | х |
| | Gait pattern | Х | | | | | |
| | GAS | Х | | | | | х |
| | GMFCS | Х | | | | | |
| Additional | AFO properties | | Х | | | Х | Х |
| measurements | Adherence | | | | х | х | х |
| | Satisfaction | | | | х | х | х |
| | | | | | | | |

 Table 2. Overview of tests performed at different measurement moments.

 $T1_k$ will be repeated for each AFO-configuration: rigid, stiff, and flexible.

**Time interval represents the number of weeks between measurement moments.

***SAM and CAPE data will be assessed in the week prior to the ticked measurement moment

AFO=Ankle-Foot Orthosis; AFO-FC=AFO footwear combination; BSS='Bronnen van Steun en Spanning'; CAPE=Children's Assessment of Participation and Enjoyment; ECWT=Energy Cost of Walking Test; FAQ=Functional Assessment Questionnaire; FMS=Functional Mobility Scale; GAS=Goal Attainment Scaling; GMFCS=Gross Motor Function Classification System; SAM=StepWatch3TM Activity Monitor.

3.4.1 Primary study parameters

Primary outcome measures in this study are:

- energy cost of walking (assessed with the Energy Cost of Walking Test (ECWT));
- the subject's daily activity (assessed with the StepWatch[™] Activity Monitor (SAM));

Energy cost of walking and walking speed

The 'capacity' qualifier of the activities and participation component describes the child's ability to execute a task or action in a standardized environment (45). In this study, activity capacity will be determined with an Energy Cost of Walking Test (ECWT). During the ECWT, subjects will walk for 6 minutes at self-preferred CWS on an indoor oval route, while oxygen uptake will be measured breath-by-breath, using the Metamax 3B portable gas analysis system (Cortex, Leipzig, Germany). Outcome measures will be walking speed (m⁻¹·min⁻¹) and EC of walking (J⁻¹·kg⁻¹·m⁻¹). EC of walking calculation will be based on the child's submaximal oxygen uptake (VO2_{submax}) and walking speed, which are both measured during a steady state of walking.

Daily activity

The 'performance' qualifier of the activities and participation component, is what a child actually does in his or her current environment (45). In this study, activity performance will be measured by monitoring the child's daily activity, using the StepWatch3[™] Activity Monitor 3.0 (SAM) (Cyma Corporation Seattle, WA, USA). The SAM is an ankle worn accelerometer that measures average amount of steps per minute over a broad spectrum of step cadences. It is an accurate, valid, reliable and feasible tool for measuring step activity in a child's current environment for both typically developing youth (TDY) (66;67) and ambulatory CP children (60). The SAM has been shown to discriminate activity levels between TDY and CP children as well as within CP children with different GMFCS levels (60). SAM data will be processed with StepWatch[™] 3.1 software © 2005. The subject's daily activity will be determined as 1) average total daily steps, 2) percentage of time children were active, 3) percentage of time children were inactive, 4) ratio of medium to low activity levels, and 5) percentage of time children show high activity levels. For adequate interpretation of the data, children will be asked to note their activity program during the day in a diary (e.g. time of getting up and type of activities after school).

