Intervention: Subjects will get an Floor Reaction Orthosis (FRO), composed out of pre-preg material (e.g. impregnated carbon fibres), which will be fabricated with integrated Neuro Swing[®] system ankle joint. This system has an adjustable spring force, alignment, and range of motion of the ankle joint. This study will investigate the effects of varying stiffness (spring force) of the AFO on gait to select the subject's optimal AFO.

Main study parameters/endpoints: Primary study parameters are energy cost of walking and the child's daily activity.

Nature and extent of the burden and risks associated with participation, benefit and group relatedness: Visits for baseline measurements (n=3) will be scheduled simultaneously with regular consultancies, to limit the number of visits to the medical center. For each AFO configuration (n=3), effects will be evaluated after four to eight weeks. Follow-up measurements will be performed for the subject's optimal AFO after twelve to twenty weeks. Baseline as well as follow-up measurements are non-invasive. Practical relevance of the study is that this extensive evaluation of AFO efficacy could contribute to improving orthotic management in CP in the (near) future.

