The primary objective of this study is to evaluate AFO efficacy in children with spastic CP on the ICF components 'body functions and structures' (i.e. biomechanics of gait) and 'activities and participation' (i.e. walking efficiency and frequency of participation).

The main research question related to this objective is: 1) what are the effects of wearing a specific AFO on biomechanics of gait, walking efficiency, daily activity and frequency of participation in children with spastic CP, whose gait is characterized by a flexed knee pattern? An additional research question is: 1a) what biomechanical changes of gait, resulting from wearing the AFO, lead to an improved walking efficiency, increased daily activity and/or frequency of participation in this specific patient group?

Secondary objective:

The secondary aim of this study is to identify prognostic factors for either a successful or unsuccessful outcome of AFO treatment on activities and participation (i.e. walking efficiency, daily activity and frequency of participation) in children with spastic CP.

The main research question for this objective is: 2) can we identify prognostic factors for a successful or unsuccessful outcome on walking efficiency, daily activity and frequency of participation after AFO treatment in children with spastic CP, whose gait is characterized by flexed knee pattern? Additional questions are: 2a) how do AFO properties (e.g. stiffness) influence the patient's gait biomechanics?; and 2b) what is the effect of gait improvements, as a result of AFO stiffness optimization, on daily activity and frequency of participation?

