3.6.3 Multivariate analysis

Evaluation of efficacy of the subject's optimal AFO will be based on analyses of pre/postintervention differences in primary and secondary outcome measures. Means of baseline measurements (T0) will be compared to evaluation measurements (T1_K) and long-term follow-up measurements (T2_{Kopt}) using a Linear Mixed Model (LMM) for repeated measures¹.

Multivariate linear regression analyses will be applied to investigate what changes in the secondary outcome measure 'biomechanics of gait' are associated with changes in primary outcome measures 'walking efficiency' and 'daily activity'. First, a stepwise univariate regression (ANOVA) will be performed to determine which factors are significantly associated with changes in biomechanics of gait. Next, significant factors will be analysed in a multivariate regression analysis model.

Multivariate regression analysis will also be applied to investigate to what extent the child characteristics and AFO properties provide determinants for success of treatment with AFOs. First, a stepwise univariate regression (ANOVA) will be performed to determine which factors are significantly associated with outcome of AFO treatment. Significant factors will be inculded in a multivariate regression model. Factors that will be analysed in the model will include baseline motor impairements, GMFCS level, gait pattern, EC of walking, physical fitness level, and AFO stiffness and neutral anlge.

¹ Participation measures (assessed with the CAPE) will only be done at baseline (T0) and at long-term follow-up (T2). Assuming that data are normally distributed, means of this outcome measure will be compared using paired samples t-test.

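### The primary outcome daily activity is five unranked StepWatch measures with no lead variable, and only energy cost is powered

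*Protocol*

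**What the plan says.** The Summary states: "Primary study parameters are energy cost of walking and the child's daily activity". Section 3.4.1 repeats the two outcomes and breaks down the second: "The subject's daily activity will be determined as 1) average total daily steps", followed by "percentage of time children were active, 3) percentage of time children were inactive, 4) ratio of medium to low activity levels" and finally "percentage of time children show high activity levels". That makes five quantities, with no composite, no order of importance and no definition of active or inactive time.

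Section 3.2.4 sizes the trial on one outcome, walking efficiency: "Sample size is based on power analyses on the expected changes in the primary outcome". It continues: "Assuming a power of 80% and a significance level of 0.05, a sample size of 29 patients is needed". This is the only significance level in the protocol.

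Section 3.6.2 compares primary and secondary outcomes across the three stiffness configurations by repeated measures ANOVA. Section 3.6.3 compares T0 with T1 and T2 "using a Linear Mixed Model (LMM) for repeated measures". Neither section gives a significance level per outcome or says whether one or both primary outcomes must be positive.

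The sentence stating the primary objective illustrates activities and participation by "walking efficiency and frequency of participation". The main research question beneath it adds daily activity.

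**The concern.** Which variable is primary is protocol content, and section 3.4.1 settles it as five co-equal quantities. A later analysis plan could set multiplicity rules, but it would start from a primary outcome that is not one variable.

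Two things are at stake. The first is error control: with five ways to show an effect on daily activity, plus energy cost, a chance finding on one of them could be reported as a primary result. If active and inactive time sum to 100%, one result could also be shown as two.

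The second is interpretation. Section 3.6.3 regresses change in daily activity on gait changes, and the secondary objective looks for predictors of success or failure on daily activity. Each needs one defined variable, since a child can improve on one SAM measure and worsen on another.

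**Working it through.** **Step 1: reproduce the protocol's figure.** Inputs from section 3.2.4: SD 1.70, difference 1.26 (25% of 5.02), significance level 0.05, power 80%, formula N = 2·SD²·(Zα+Zβ)²/Δ².

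- Two-sided: 2 × 1.70² × (1.960 + 0.842)² / 1.26² = 28.58, rounded up to 29. This matches.
- One-sided: 22.51, rounded up to 23. This does not match, so the 0.05 is two-sided. All of it is spent on energy cost.

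**Step 2: count the tests.** Energy cost plus five SAM measures makes six. If percentage active and percentage inactive sum to 100%, a change in one is the exact negative of the change in the other. Their two-sided p-values are then identical, leaving five distinct tests.

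**Step 3: family-wise error, independent tests.** The assumptions are mine, not the protocol's: every measure tested at 0.05, one contrast per measure, any one positive result counted as success.

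- Five distinct tests: 1 − 0.95⁵ = 22.6%.
- For comparison, energy cost plus one SAM measure: 1 − 0.95² = 9.75%.

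**Step 4: allow for correlation.** The protocol gives no correlations, so a range is assumed: 0 to 0.95 among the SAM measures and 0 to 0.5 between each of them and energy cost. Two-sided one-sample t-tests on change scores were simulated under no effect, with n = 29, five distinct tests and 40,000 replicates per setting (standard error about 0.2 percentage points).

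| Correlation among SAM measures | Energy-cost correlation 0 | 0.3 | 0.5 |
|---|---|---|---|
| 0 | 22.6% | – | – |
| 0.5 | 19.7% | 19.2% | 18.7% |
| 0.7 | 17.6% | 16.9% | 16.4% |
| 0.8 | 16.1% | 15.4% | 14.9% |
| 0.9 | 14.0% | 13.6% | 13.1% |
| 0.95 | 12.8% | 12.3% | 11.7% |

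The range is 11.7% to 22.6%, or about 12% to 23%.

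**Step 5: what is left out.** The table counts one contrast per measure. Testing T0 separately against T1 and T2, with any positive contrast counted, would add to it.

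**Step 6: price of the alternatives, by the protocol's own formula.**

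- Bonferroni over two primary outcomes (0.025 each): 34.6, so N = 35.
- Bonferroni over all six measures (0.0083 each): 44.1, so N = 45.
- Fixed order with energy cost first: energy cost keeps 0.05, so N stays at 29.

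Both Bonferroni options exceed the planned 32.

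**The case against.** The strongest objection is that the protocol never states the decision rule. The 0.05 appears once, for the energy-cost sample size, and nothing says that any one positive measure is enough. Multiplicity handling is commonly left to the analysis plan, which is not at hand. This stands, and it makes the error rate conditional. It does not remove the defect, which is that section 3.4.1 makes five unranked quantities one primary outcome.

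Three stronger readings are tempting, and the document does not support them.

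- **An error rate near 27%.** Six independent tests give 1 − 0.95⁶ = 26.5%, but that counts active and inactive time as independent. If they are complements, the ceiling is 22.6%.
- **Active and inactive time are certainly the same number.** Section 3.4.1 defines neither, nor their denominator, so they could fail to sum to 100%.
- **The primary objective ignores daily activity.** Only the parenthesis in the objective sentence omits it. The main research question under the same heading names it, and the Summary and section 3.4.1 agree on the two primary outcomes.

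It can also be said that this is a single-centre pre-post study of 32 children aimed at working mechanisms, so a pass/fail error rate carries less weight than in a confirmatory trial. That is fair and limits the severity. The protocol nevertheless declares primary outcomes and powers one of them at 0.05.

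Finally, section 3.4.1 treats energy cost as capacity and daily activity as performance. A fixed order puts the second behind the first, which is a real cost.

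**Conclusion.** The point holds in a limited form and should be corrected. Daily activity is primary through five unranked SAM measures, two of them apparently complements. No lead measure is named, and only energy cost is powered.

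The error rate of about 12% to 23% rests on four assumptions that the protocol does not state: each measure tested at 0.05, any one positive result sufficient, one contrast per measure, and the correlations in the table. Under them, even the low end is more than twice 5%. Energy cost stays interpretable as a primary outcome in its own right. A claim on daily activity does not, until one variable is named. The wording of the objective is a minor inconsistency.

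**What to change.** In section 3.4.1, name one SAM variable as primary and make the other SAM summaries secondary. Average total daily steps is an example because it is listed first, but that is not a ranking and the choice is the investigators'. Define active and inactive time, and report them as one measure if they sum to 100%.

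In section 3.6.3, name one primary contrast per outcome, for example T2 against T0. Test in fixed order: energy cost at two-sided 0.05, then the chosen SAM variable at two-sided 0.05 only if energy cost is significant. With one contrast each, this holds the family-wise error at 5%. Without a named contrast it does not.

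Align the parenthesis in the primary objective with the two primary outcomes.

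The cost is a few lines of text, with no change to data collection or to the sample size of 29 (32 planned). The other SAM summaries lose primary status, and daily activity has no confirmatory test if energy cost is not significant. The SAM variable also remains unpowered, which the protocol should say.
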